4.6 Rationale for Public Health Emergency mitigation procedures

During a Public Health emergency as declared by Local or Regional authorities i.e. pandemic, epidemic or natural disaster, mitigation procedures to ensure subjects afety and trial integrity are listed in relevant sections. Notification of the Public health emergency should be discussed with Novartis prior to implementation of mitigation procedures, and permitted/approved by Local or Regional Health Authorities and Ethics Committees as appropriate.

5 Population

This study will enroll adult subjects, 18 years of age or older with at least 6 months history of physician diagnosed moderate to severe dry eye disease in both eyes as defined by entry criteria.

It is estimated that approximately 800 subjects will need to be screened in Part 1 to have approximately 680 subjects randomized into the 56-day treatment period. Enrollment in the study will remain open until a sufficient number of evaluable subjects is achieved in Part 1.

For Part 2, it is estimated that up to 200 subjects will need to be screened to randomize up to 160 subjects into the 2 treatment arms.

Subjects discontinuing the study after randomization in either Part 1 or Part 2 will not be replaced, and subjects who discontinue the study in Part 1 will no longer be eligible for Part 2.

For subjects who discontinue treatment but do not discontinue the study during Part 1, or for subjects who experience a treatment related adverse event (AE) or serious adverse event (SAE), eligibility for Part 2 will be dependent on the reasons for treatment discontinuation or nature of the AE/SAE. The decision for participation in Part 2 will be at the discretion of the Investigator, with guidance from the Sponsor as needed.

The following inclusion/exclusion criteria apply to screening of subjects in Part 1, as well as screening and baseline in Part 2.

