5.2 Exclusion criteria

Subjects meeting any of the following exclusion criteria at the Screening Visit in Part 1 are not eligible for participation in the study.

Subjects meeting any of the following exclusion criteria at the Screening and Baseline Visits in Part 2 are not eligible for participation in Part 2 of the study.

- 1. Ocular infection (bacterial, viral, or fungal) in either eye within 30 days prior to Screening
- 2. Use of artificial tears, gels, lubricants within 4 hours of conducting assessments at the Screening Visit
- 3. Use of contact lenses in either eye within 14 days of Screening, and any use of contact lenses for the duration of the study
- 4. Subjects with **uncontrolled** ocular rosacea (affecting the eye adnexa), posterior blepharitis or Meibomian gland dysfunction

NOTE: Controlled is defined as a stable condition, not as an asymptomatic condition. If the subject is doing lid scrubs and/or warm compresses to control these conditions, they must continue with their normal regimen. However, subjects must have been utilizing these therapies for at least 30 days prior to Screening, no new regimens added during the course of the study, and no current regimens discontinued during the study.

- 5. Clinically significant conjunctivochalasis in either eye defined as an excessive redundancy of the conjunctiva that obliterates the inferior tear meniscus and/or rolls over the lower lid margin seen upon routine ocular exam or apparent with normal lid closure
- 6. Corneal conditions, other than dry eye related corneal epitheliopathies, affecting the corneal structure of either eye including but not limited to:
 - Clinically significant corneal dystrophies defined as affecting the structure of the corneal surface, affecting best-corrected visual acuity, or is an actively changing or unstable condition
 - Corneal scars with residual corneal surface irregularity
 - Pterygia that extend > 2mm onto the corneal surface, or are elevated rather than flat, or show concentrated staining
 - Keratoconus
- 7. Any history of ocular herpes simplex virus or herpes zoster virus infection, or other severe ocular conditions such as graft versus host disease, Stephen's Johnson Syndrome, sarcoidosis

- 8. Currently active, or history of ocular allergies during the time of year the subject will be participating in the study
- 9. History of hypersensitivity to ECF843, staining reagents (fluorescein sodium or lissamine), or their excipients.

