- 10. Subjects with current punctal plugs or punctal cauterization or occlusion
- 11. Chronic medications (both over the counter and prescription) that have not been stable for at least 30 days prior to Screening. Subjects who have any anticipated change in their chronic medication regimen are excluded until the new regimen has been stable for at least 30 days.

NOTE: chronic refers to medications taken on a specific regimen which includes medications that may not be taken daily (e.g., bisphosphonates given once per month). Pro re nata (PRN) medications such as low dose acetaminophen (e.g., Tylenol) and over the counter Non Steroidal Anti Inflammatory Drugs (NSAIDs) are not excluded.

- 12. Use of Restasis[®], Cequa[®], or Xiidra[®] within 30 days prior to Screening
- 13. Medical device use to treat meibomian gland dysfunction (e.g., LipiFlow, Intense Pulse Light Therapy, or similar) within 3 months prior to Screening
- 14. Use of ocular, nasal, inhaled, or systemic corticosteroids within 30 days of Screening (low dose over-the-counter steroid creams applied to the skin are acceptable), or any use during the duration of study participation
- 15. Any history of corneal refractive surgery (e.g., laser-assisted in situ keratomileusis [LASIK], photorefractive keratectomy [PRK], etc)
- 16. Any intraocular surgery including cataract surgery within 6 months prior to Screening
- 17. Chronic systemic disease that was diagnosed within the last 30 days or that has not been stable for at least 30 days prior to the Screening
- 18. Use of other investigational drugs within 5 half-lives of enrollment, or within 30 days, or until the expected pharmacodynamic effect has returned to baseline, whichever is longer
- 19. History of malignancy of any organ system (other than localized basal cell carcinoma of the skin or in situ cervical cancer), treated or untreated, within the past 5 years, regardless of whether there is evidence of local recurrence or metastases
- 20. Subjects demonstrating any medical condition (systemic or ophthalmic) that may, in the opinion of the Investigator, preclude the safe administration of test article or safe participation in this study, or potentially impact the outcome of the study
- 21. Pregnant or nursing (lactating) women

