Period Treatment Screening Visit Name Visit 1-Screening Visit 2 Visit 3 Visit 4 Visit 5/EOS Visit 1-Randomization 28 Days 1 14 42 56 1 Informed consent Х Х Inclusion / Exclusion criteria Demography Х Medical history/current medical conditions X Concomitant medications Х Х Х Х Х Pregnancy Test (urine) Х Х Х In office SANDE score Х Corrected visual acuity Х Х Х Х х Х Х х Х Slit lamp biomicroscopy Х Ocular hyperemia Х Х Х Х Tear break-up time (TBUT) Х Х Х Х Х х Corneal fluorescein staining² Х Х Х Х Х Х Х Х Х Conjunctival lissamine staining Schirmer Tear Test Х Intraocular Pressure (IOP) Х Х Х Х Х Fundus Exam Х Х Contact IRT³ Х Х Х Х Randomization Х Dispense study medication Х Х Х Х Х In-office study drug administration

Table 8-1 **Assessment Schedule, Part 1**

Novartis	Confidential	
Amended Protocol Version 01 (Clean)		Pro

Page 39 Protocol No. CECF843A2201

Period	Screening	Treatment						
Visit Name	Visit 1-Screening	Visit 1-Randomization	Visit 2	Visit 3	Visit 4	Visit 5/EOS		
Days	1	1	14	28	42	56		
Adverse Events	Х	x	Х	Х	Х	Х		
At home SANDE questionnaire (eDiary) ⁴	Х		Х	Х	Х			
Study completion information						Х		
X Assessment to be recorded in the clinica	l database or received e	ectronically from a vendor			•	÷		

3 Sites will enter average SANDE score (obtained from the electronic diary) and the corneal fluorescein staining score from the eye with the highest composite score (sum of the 5 regions)

4 Subjects will complete an electronic diary once daily (in the evening before bed time and prior to the evening dose of study medication) from Visit 1-Screening through to the end of the study (at home SANDE questionnaire)

Table 8-2Assessment Schedule, Part 2

Period	Screening	Treatment	eatment						Post Treatment Follow-up		
Visit Name	Visit 1	Visit 2	Visit 3	Visit 4	Visit 5	Visit 6	Visit 7/ EOT	Visit 8/ EOS ⁸	Safety F/U EOS ⁸ +4. +8, +12 Weeks		
Days	-14	1	7	14	28	42	84	126	154, 182, 210		
Informed consent	х										
Inclusion / Exclusion criteria	x	x									
Demography	Х										
Medical history/current medical conditions	x										
Concomitant medications	x	x	x	x	x	x	x	x	x		
Pregnancy Test (urine)	Х						X				

Period	Screening	Treatment						Post Treat	tment Follow-up
Visit Name	Visit 1	Visit 2	Visit 3	Visit 4	Visit 5	Visit 6	Visit 7/	Visit 8/ EOS ⁸	Safety F/U EOS ⁸ +4. +8, +12 Weeks
Days	-14	1	7	14	28	42	EOT 84	126	154, 182, 210
In office SANDE score	X	X		14	20	72	04	120	134, 102, 210
Corrected visual acuity		Х					Х		
				.					

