Slit lamp biomicroscopy	х	Х	Х	х	х	Х	Х		
Ocular hyperemia		х	Х	х	х	Х	Х		
	1								
Tear break-up time	x	x			х		x		
(TBUT)									
Corneal fluorescein staining ³	х	х	х	х	х	x	х		
staining									
Conjunctival lissamine									
staining	Х	х	Х	Х	Х	Х	Х		
Schirmer Tear Test	Х	x							
Intraocular Pressure				-					

Novartis Amended Protocol Version 01 (Clean)

Page 40 Protocol No. CECF843A2201

Confidential

Period	Screening	Treatment						Post Trea	tment Follow-up
Visit Name	Visit 1	Visit 2	Visit 3	Visit 4	Visit 5	Visit 6	Visit 7/ EOT	Visit 8/ EOS ⁸	Safety F/U EOS ⁸ +4. +8, +12 Weeks
Days	-14	1	7	14	28	42	84	126	154, 182, 210
Fundus exam		Х					Х		
Randomization		Х							
Dispense study drug	Х	Х		Х	Х	Х			
In-office study drug administration		х		х	x	x			
Adverse Events ⁶	х	Х	Х	Х	Х	Х	Х	Х	Х
At home SANDE questionnaire (eDiary) ⁷	x	x	x	x	x	x			
Study completion							x		
X Assessment to be reco	orded in the clir	nical database	or received ele	ctronically from	n a vendor				

Novartis Amended Protocol Version 01 (Clean)

Confidential

Page 41 Protocol No. CECF843A2201

Period	Screening	Treatment		Post Treatment Follow-up					
Visit Name	Visit 1	Visit 2	Visit 3	Visit 4	Visit 5	Visit 6	Visit 7/ EOT	Visit 8/ EOS ⁸	Safety F/U EOS ⁸ +4. +8, +12 Weeks
Days	-14	1	7	14	28	42	84	126	154, 182, 210
	plete an electronic d isit 1 (Screening) th				aily (in the eve	ning before be	d time and pric	r to the evenin	ng dose of study

Novartis Amended Protocol Version 01 (Clean)

Page 42 Protocol No. CECF843A2201

Confidential

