8.1 Screening

No subjects may be re-screened if they fail entry criteria for any reason other than required stabilization time frames for medications and/or medical history.

If a subject is enrolled and it is determined prior to the completion of Visit 1 that the subject did not meet criteria pertaining to:

- duration of DED diagnosis;
- time frame required for stabilization of chronic medications or therapies, time frames related to medical history or use of contact lenses

the subject will be screen failed and brought back at a later date to re-attempt the screening process once the proper time frames have been achieved.

In the case of re-screening, the subject will receive a new subject number and all screening assessments required at Visit 1 must be completed on the day of randomization, regardless if the assessments were conducted at the previous screening visit.

Re-screening is only allowed one time for a particular subject and per part of the study. Rescreening must not be used as a method to force subject eligibility into the study.

For subjects requiring washout of prior medications or contact lenses, informed consent must be obtained prior to washout. Subject will be enrolled into the study and brought back for screening assessments (Visit 1) after the washout is completed.

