8.4.2 Pregnancy

A urine pregnancy test will be conducted for all women of childbearing potential to assess pregnancy as indicated in the Schedule of Assessments.

Additional pregnancy testing might be performed if requested by local requirements.

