10.1.4 Pregnancy reporting

If a female trial subject becomes pregnant, the study treatment should be stopped, and the pregnancy consent form should be presented to the trial subject. The subject must be given adequate time to read, review and sign the pregnancy consent form. This consent form is necessary to allow the investigator to collect and report information regarding the pregnancy. To ensure subject safety, each pregnancy occurring after signing the informed consent must be reported to Novartis within 24 hours of learning of its occurrence. The pregnancy should be followed up to determine outcome, including spontaneous or voluntary termination, details of the birth, and the presence or absence of any birth defects, congenital abnormalities, or maternal and/or newborn complications.

Pregnancy should be recorded and reported by the investigator to the Novartis Chief Medical Office and Patient Safety (CMO&PS). Pregnancy follow-up should be recorded on the same form and should include an assessment of the possible relationship to the ECF843 treatment to any pregnancy outcome. Any SAE experienced during pregnancy must be reported.

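### Part 2 re-applies the pregnancy exclusion at Baseline, when ECF843 starts, but schedules no pregnancy test at that visit

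*Protocol*

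**What the plan says.** Protocol Section 5 introduces the criteria with "The following inclusion/exclusion criteria apply to screening of subjects in Part 1, as well as screening and baseline in Part 2". Section 5.2 repeats this for the exclusions: subjects meeting "any of the following exclusion criteria at the Screening and Baseline Visits in Part 2 are not eligible". Exclusion 21 is "Pregnant or nursing (lactating) women". SAP Section 1.1.2 also has eligibility checked again at Part 2 Visit 2 before randomization, and the inclusion/exclusion row of Table 8-2 is marked at Visits 1 and 2.

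Visit 2 (Day 1) follows a 14-day vehicle run-in. Table 8-2 places randomization there, and SAP Section 2.1.1.2 places the first randomized dose there. Subjects coming from Part 1 must have received vehicle only (Protocol Section 3), so Visit 2 is their first possible ECF843 dose in this study. The same holds for subjects who enter directly into Part 2.

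On testing, Section 8.4.2 says that a "urine pregnancy test will be conducted for all women of childbearing potential to assess pregnancy as indicated in the Schedule of Assessments", with further tests only where local requirements ask for them. In Table 8-2 the pregnancy row is marked at Visit 1 (Day -14) and Visit 7/EOT (Day 84) and nowhere else.

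**The concern.** The protocol makes pregnancy status an eligibility condition on the day ECF843 starts, but the schedule supplies no measurement of it that day. A pregnancy too early to detect at Day -14, or one that began early in the run-in, would reach first ECF843 exposure without a scheduled test.

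The protocol treats the fetal risk as unknown (Sections 4.5 and 7). Section 10.1.4 adds: "If a female trial subject becomes pregnant, the study treatment should be stopped". Stopping depends on someone knowing about the pregnancy, and after Day -14 no scheduled test would reveal it until the end of treatment.

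Part 1 does not raise the same question, because Table 8-1 puts screening and randomization on the same day. Part 2 separates them by the run-in. What is at stake is participant safety and the verification of one eligibility criterion; the statistical analysis is not involved.

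**Working it through.** There is no planned figure to reproduce. The check is a reading of the schedule plus day counts.

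**Marks in Table 8-2 (Protocol)**

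| Row | Visits marked |
|---|---|
| Inclusion/exclusion criteria | 1, 2 |
| Randomization | 2 |
| Urine pregnancy test | 1, 7 |

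Counting cells across the pregnancy row puts the second mark under Visit 7/EOT. Neighbouring rows do carry a Visit 2 mark, so a shifted column is unlikely. The row label has no footnote marker, although some table footnotes are missing from the public copy.

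**Day counts (SAP Section 2.1.1.4)**

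- Before baseline, study day = visit date - first-dose date. Day -14 is therefore 14 days before the first randomized dose.
- From baseline on, study day = visit date - first-dose date + 1. Day 84 is therefore 84 - 1 = 83 days after the first dose.

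| Interval (nominal days) | Current schedule | With a Visit 2 test |
|---|---|---|
| Last scheduled test to first randomized dose | 14 | 0 |
| First dose to next scheduled test | 83 | 83 |
| Longest gap between scheduled tests | 14 + 83 = 97 | 83 |

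**Who is affected.** Part 2 randomizes up to 160 subjects 3:1, so up to 160 x 3/4 = 120 receive ECF843. Only the women of child-bearing potential among them are concerned, and the documents do not give that number.

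**Whether other text supplies a test at Visit 2.** Section 8.1 says that "all screening assessments required at Visit 1 must be completed on the day of randomization", but this applies to re-screened subjects only. Section 8.4.2 leaves extra tests to local requirements. The contraception requirement governs behaviour and does not establish pregnancy status. None of these puts a protocol-wide test at Visit 2.

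**The case against.** The strongest reply is that the documents do not contradict each other. Exclusion 21 names no test and no time limit, so it can be re-checked at Visit 2 by questioning, as nursing or medication stability would be. Section 8.4.2 defers to the schedule, and the schedule is clear. That is right, and the point should not be put as an inconsistency. Questioning, however, cannot be relied on to reveal an early, unrecognised pregnancy.

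The second reply is that the risk is already limited. Effective contraception is required, and oral contraceptives must have been stable for 3 months before investigational drug. Only vehicle is given before Day 1. ECF843 is about 450 kDa and was not quantifiable in monkey serum after 7 days of dosing up to six times daily (Section 4.2). All of this stands and keeps the point minor. A Visit 2 test would also leave 83 days on treatment without a scheduled test.

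A reader might go further and infer that the empty cell must be an oversight, because TBUT, corneal staining and the "Schirmer Tear Test" are all repeated at Visit 2. The documents do not support that inference. SAP Section 2.3.2 lists all three as baseline characteristics to be summarized for FAS2, and TBUT and staining are also efficacy assessments that need a baseline. Their inclusion criteria carry numeric cut-offs that require measurement, whereas exclusion 21 has none. Their Visit 2 marks therefore do not show that the pregnancy test was forgotten.

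**Conclusion.** The point holds as a minor safety gap. Part 2 re-imposes the pregnancy exclusion at first ECF843 exposure, but the last scheduled test is nominally 14 days old by then and the next comes 83 days after the first dose.

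A reader might also infer that exposed pregnancies are to be expected in this trial. The documents give neither the share of women of child-bearing potential nor a contraceptive failure rate for the enrolled population, so the number of exposures that a Visit 2 test would prevent cannot be estimated from them. With at most 120 ECF843 subjects, mandatory contraception and minimal expected systemic exposure, the gain is real but small. No endpoint, estimate or power figure changes.

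The conclusion assumes that visits occur on their nominal days, that Table 8-2 in the public copy shows the row correctly, and that no missing footnote adds a test at Visit 2.

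**What to change.** Two edits to the protocol:

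- Table 8-2, urine pregnancy test row: add a mark at Visit 2 (Day 1).
- Section 8.4.2, add: *In Part 2, a negative urine pregnancy test at Visit 2 is required for women of child-bearing potential before randomization and the first dose of randomized study treatment.*

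The word *randomized* before *study treatment* matters. The glossary counts controls as study treatment, and run-in vehicle is dispensed at Visit 1, so without that word the condition would refer to a dose taken before Visit 2.

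The cost is one additional urine test per woman of child-bearing potential, at a visit that already takes place and with a test already used in the study. The change needs a written amendment with sponsor and IRB/IEC approval, and health-authority approval where required (Section 14.1). Part 2 cannot begin until Part 1 has been completed and analysed, so this can be done before Part 2 screening. The added test would still miss very recent conceptions.

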6.1 Study treatment

Part 1

Subjects will receive double-masked treatment for 56 days.

Part 2

Subjects will receive double-masked treatment for 84 days after a 14-day ECF843 vehicle runin period.

6.1.1 Investigational and control drugs

Investigational/ Control Drug	Pharmaceutical Dosage Form	Route of Administration	Presentation	Sponsor (global or local)
(Name and Strength)				
ECF843 0.15 mg/ml	Liquid as drops single-dose ophthalmic	Topical ocular	Double masked	Global
ECF843 0.45 mg/ml	Liquid as drops single-dose ophthalmic	Topical ocular	Double masked	Global
ECF843 Vehicle	Liquid as drops single-dose ophthalmic	Topical ocular	Double masked	Global

 Table 6-1
 Investigational and control drug

ECF843 active and vehicle will be packed as double masked kits. Each kit will consist of a carton containing 6 aluminum foil pouches to protect the product from light, and each pouch will contain 3 blow-fill-seal (BFS) containers for single use. IRT will instruct on the number of kits to be dispensed. A sufficient number of kits will be dispensed per visit to cover the required treatment period between visits.

6.1.2 Additional study treatments

No other treatment beyond investigational drug and control drug are included in this trial.

6.1.3 Treatment arms/group

In Part 1, subjects will be screened and assigned to one of the following five masked treatment arms/groups in a ratio of 1:1:1:1:1.

- ECF843 0.45 mg/mL TID or vehicle
- ECF843 0.15 mg/mL TID or vehicle
- ECF843 vehicle TID
- ECF843 0.15 mg/mL BID or vehicle
- ECF843 vehicle BID

In Part 2, following a 2-week run-in phase with vehicle, subjects will be assigned at Visit 2 to one of the following two masked treatment arms/groups in a ratio of 3:1.

- ECF843 (concentration and dosing frequency to be determined from Part 1)
- ECF843 vehicle (dosing frequency to be determined from Part 1)

6.1.4 Treatment duration

The planned duration of double-masked treatment during Part 1 is 56 days. In Part 2, a 14-day open label vehicle run-in will be followed by 84 days of masked treatment. Subjects may be discontinued from treatment earlier due to unacceptable toxicity, disease progression and/or treatment is discontinued at the discretion of the investigator, Sponsor, or the subject. Refer to Section 9.1 on discontinuation from the study for additional details.

6.2 Other treatment(s)

6.2.1 Concomitant therapy

All prescription and over-the-counter medications, procedures, and significant non-drug therapies (including physical therapy and blood transfusions) administered after the subject was enrolled into the study must be recorded on the appropriate electronic Case Report Forms (eCRFs). Concomitant topical ocular medications for reduction of intraocular pressure are permitted.

Each concomitant drug must be individually assessed against all exclusion criteria/prohibited medication. If in doubt, the investigator should contact the Novartis medical monitor before randomizing a subject or allowing a new medication to be started. If the subject is already enrolled, contact Novartis to determine if the subject should continue participation in the study.

